2. Reporting poor self-care on screening (Health Self-Care Neglect Scale, score ≥ 2)
3. Able to complete the protocol, e.g., adequate vision and hearing, English speaking
4. Caregiver of a patient diagnosed bvFTD

3. Key Exclusion Criteria:

1. Participation in another support RCT
2. Untreated major psychiatric illness (Use of anti-anxiety/anti-depressant medicines is acceptable and will be adjusted in analysis if group imbalance is identified.)
3. Caregiver with Cognitive Impairment based on Telephone Interview for Cognitive Status (TICS) score <25

4. Subject Recruitment and Screening:

We will enroll a consecutive sample of informal bvFTD caregivers identified from the Penn Frontotemporal Degeneration Center (<https://ftd.med.upenn.edu>), one of the largest NIH-funded centers dedicated to the study of young-onset dementias in the United States and a site where [name] is PI of other FTD-related studies. The Penn FTD Center is actively studying 110 bvTD patients, all of whom have caregivers and we see approximately 20 bvFTD patients a year. If recruitment is slower than expected, we will identify caregivers through the Association for Frontotemporal Degeneration, a national caregiver organization, with whom [name] works closely.

To obtain a consecutive sample we will seek a HIPAA waiver to screen the FTD Center clinic daily appointment schedule to identify every patient with a potentially eligible caregiver. FTD Center clinic providers and staff will identify potential caregiver participants (e.g., speak English) and determine their interest in speaking with research staff about the study. If caregivers agree to speak with research staff, the RA will explain the study and screen the caregiver for inclusion and exclusion criteria with standardized testing (e.g., Health Self-Care Neglect scale) and interview (e.g., hearing). Fully eligible caregivers who provide informed consent (see Human Subjects) will complete the virtual baseline assessment before being randomized to study arm. After all baseline data are collected, the caregiver will be randomized to study arm. At that time, participants will be trained in tablet use and how to access the Health Information website.

To safeguard confidentiality and privacy we have planned a 2 step screening process:

1. The RA will obtain Verbal Consent from interested caregivers to conduct preliminary screening for eligibility using study inclusion and exclusion criteria:

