Fully eligible caregivers who provide informed consent will complete the baseline assessment before being randomized to study arm. The Project Manager will open a numbered sealed envelope, prepared by the team in advance, which assigns caregivers to their study arm. The Project Manager will then notify the study staff and participants of their group assignment (ViCCY or HI only) by telephone, email or message. The Project Manager will notify the study staff and participants of their group assignment (ViCCY or HI only) by telephone, email or message, as preferred by the individual. Although balance in sample size can be achieved with block randomization, the groups may not be fully comparable on other factors. Initial comparison of the groups will allow us to control for important covariates in the analyses. Investigators and all staff involved in collecting assessment data will be blinded to group assignment until after the data are locked. The Health Coaches providing the intervention and the caregiver participants will not be blinded. All baseline data will be collected prior to randomizing. Timing of follow-up assessments will be based on day of randomization

4. Administration of Surveys and/or Process:

We will enroll 30 informal bvFTD caregivers and the bvFTD patients for whom they care. After collecting baseline data, we will block randomize the caregivers 1:1 to the intervention or control group, stratifying randomization by caregiver sex and relationship to the patient (e.g., spouse, adult child) factors known to influence caregiving burden, perceived stress, and receptivity to the intervention.

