We will provide tablet devices with wireless network access and connect caregivers in both conditions to the Internet so they can access the Internet site providing Health Information (HI) content for 6 months of the study. A data plan will be provided and is included on the tablets. Research staff will provide instruction on how to use the tablet and how to access the HI website. A research diary will also be provided to aid tracking of healthcare resources used and costs. Participating caregivers in both study arms will be encouraged to spend at least 30 minutes weekly using the Internet modules or books for six months. Those who choose to use books rather than the website will be asked to keep track of the number of book chapters reviewed each month. Use of the website or book chapters will be used as a measure of fidelity in both arms. After six months, we will collect all tablet devices (both groups) to minimize bleeding of the intervention into the follow-up period, and we will continue to track use of the website to identify if bleeding occurs.

In addition to augmented standard care HI, caregivers randomized to ViCCY will receive 10 front-loaded sessions of virtual health coaching by trained RNs over the first 6 months with content based on the theoretical framework and our prior research. Health coaching sessions will be provided through the tablets via Zoom conferencing software. Sessions are weekly initially and decrease in frequency over time. Because maintaining contact is important to the success of stress reduction interventions, the assigned Health Coaches will check in with caregivers between intervention sessions. We will offer booster sessions to any caregiver in the ViCCY arm who wishes to receive additional support during the 6-month intervention interval. We will track the number of sessions and test for differential effectiveness based on the dose received. If a brief check-in call becomes an intervention session, it will be tracked for use in analysis. We will mail monthly newsletters to maximize retention.

5. Data Management:

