Assessments of self-care, perceived stress, depression, burden, coping, relationship quality, and health status will be conducted at baseline (after enrollment but prior to randomization) and by phone at 3 and 6 months. We will also collect the credibility-expectancy scale at 1 month to evaluate treatment expectancy. Using contrasts within a mixed-effect modeling framework, we will assess intervention efficacy at 6 months using intention-to-treat analysis. We provide 10 health coaching sessions based on pilot data and literature demonstrating that a shorter duration of health coaching is not routinely effective. We chose to assess the primary aim at 6 months based on prior psychosocial intervention studies, but we will also assess outcomes at 3-months based on this rationale: baseline (enrollment), to generate consistent profiles of all enrollees at a consistent point in time and prior to implementation of the intervention; at 3-months to evaluate very early effects; and at 6-months to demonstrate efficacy of the intervention. Our goal is to establish preliminary efficacy and in a future study we will evaluate longer terms effects of ViCCY vs. HI at 6-months.

If a subject can no longer participate in the study safely or due to changes in circumstance that prevents participation (e.g., imprisonment, long term hospitalization, etc.) they will be withdrawn from the study. Data collection will not continue for participants who are withdrawn from the study. If applicable, research staff will arrange to collect study equipment from the participants who are withdrawing.

STUDY PROCEDURES:

1. Detailed Description:

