We will use a RCT design to achieve robust and unbiased results, as detailed below. We will enroll 30 informal bvFTD caregivers and the bvFTD patients for whom they care. After collecting baseline data, we will block randomize the caregivers 1:1 to the intervention or control group, stratifying randomization by caregiver sex and relationship to the patient (e.g., spouse, adult child) factors known to influence caregiving burden, perceived stress, and receptivity to the intervention. We will provide tablet devices with wireless network access and connect caregivers in both conditions to the Internet so they can access the Internet site providing Health Information (HI) content, which will be the only content provided to caregivers in the control group. In addition to HI, the intervention group will receive 10 front-loaded sessions of ViCCY over 6 months. To safeguard confidentiality, tablets provided to caregivers can only be used for the study. Assessments of self-care, perceived

stress, coping, and health status will be conducted at baseline (after enrollment but prior to randomization) and by phone at 3 and 6 months. Using contrasts within a mixed-effect modeling framework, we will assess intervention efficacy at 6 months using intention-to-treat analysis. We chose to provide 10 health coaching sessions based on our pilot data and literature demonstrating that a shorter duration of health coaching is not routinely effective. We chose to assess the primary aim at 6 months based on prior psychosocial intervention studies, but we will assess outcomes at 3-months based on this rationale: baseline (enrollment), to generate consistent profiles of all enrollees at a consistent point in time and prior to implementation of the new intervention; at 3-months, very early effects, at 6-months longer-term effects of ViCCY. We will pull resource use data from the electronic medical record (EMR) in 30-day increments and validated these data during routine follow-up calls with caregivers. We expect the proposed study to require 5 years for completion.

2. Data Collection:

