The Project Manager will identify training requirements relevant to the study activities and develop a training plan and process for providing and documenting training activities. This includes developing training materials (checklists, manuals, slides, and FAQs) and implementing a process for tracking. She will oversee participant enrollment, data collection, data entry and cleaning, and analysis efforts to assure that these activities take place as planned. In addition, a clinical research coordinator will be hired to facilitate smooth and efficient data collection, help with recruitment and identification of potential subjects.

Health coaches. We will hire 2-3 experienced health coaches with excellent interpersonal communication skills, and comfort with technology. The coaches will receive two days of initial training in health coaching from [name] and her team and then completed 7 hours of online training in motivational interviewing provided by the University of Colorado, College of Nursing. [name] will also provide the coaches with a day of training related to FTD and they will receive the book, "What if it's Not Alzheimer's," developed for FTD families, which contains a chapter written by [name] on common behavioral symptoms in persons with FTD. Thereafter, weekly training and supervision will be conducted by Drs. [name], [name] and [name] as the coaches begin sessions with the caregivers. As part of this supervision, audio-recordings of coaching sessions will be reviewed by independent raters using the Behavior Change Technique taxonomy. Two trained raters have judged randomly selected session recordings for each coach, assessing completeness and thoroughness of the therapeutic techniques used. We will continue to assess the quality of the coaching as we add this group of caregivers with unique issues.

Internet Access. We will leverage the current technology infrastructure from R01NR01819. We will provide tablet devices to all participating caregivers. Tablets are versatile, allowing privacy for coaching sessions and website access to those in the HI group. The tablet uses an embedded computer camera capable of full 2-way duplex video and audio transmissions for real-time communication. Existing broadband Internet connection is not required because we supply devices with mobile connectivity. Technology experts (Caryl Technologies, with whom the team currently work) will train research staff to set up

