Internet service and devices with Caregivers during a virtual visit. Caregivers will be left with a step-by-step manual and the research assistant phone number in case technology issues occur.

Data Coordinating Center - Data coordination for the trial will be done by the BECCA (Biostatistics * Evaluation * Collaboration * Consultation * Analysis) Lab in the School of Nursing. The BECCA Lab is comprised of a team of highly skilled doctoral and masters level statisticians, along with Penn Nursing research assistants and biostatistics graduate interns who oversee data management and analytic activities. The lead statistician and Co-Investigator, [name] will ensure statistical rigor and appropriateness of all analyses.

Research Technology staff will develop and maintain a REDCap data management system. They will collaborate with the investigators to identify relevant clinical data from electronic medical record data (EMR) in the Penn Data Store and design, test and implement a process to import data at a scheduled frequency to data tables, which will be part of the research database. Research Technology staff will also develop programs to identify new hospital encounters for study participants using EMR information in order to initiate communication to the research staff that follow up action may be required.

Data Management staff will develop the case report forms and modify standard or template questionnaires as needed. They will design and develop the trial database and required modules. All research data for the trial will be stored in an electronic database that is managed by BECCA Lab. The database will be hosted on secure School of Nursing computing servers with access restricted to only those individuals who are authorized to work on the trial. Individual user accounts with passwords will be used to restrict access to the database. Specific privilege assignments within the database will be employed to limit the types of functions that authorized users can perform to those functions that are appropriate for their role in the trial. Additional measures to prevent unauthorized external access to the database environment will be employed using network firewall technologies.

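### The research assistant is the caregivers' contact for tablet problems, so a support call about video coaching can reveal the arm to an outcome collector, and nothing in the plan prevents it

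*Combined protocol and SAP*

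**What the plan says.** All places are in the combined protocol and SAP.

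- **Help line.** Resources Necessary for Human Research Protection, Internet Access: "Caregivers will be left with a step-by-step manual and the research assistant phone number in case technology issues occur". The sentence is not limited to one arm.
- **Blinding.** Methods, 3. Method for Assigning Subjects to Groups: "Investigators and all staff involved in collecting assessment data will be blinded to group assignment until after the data are locked". The same section names the coaches and the caregivers as unblinded.
- **Who collects outcomes.** Risk/Benefit Assessment, 1. Risks (the Fatigue and Stress paragraphs) describes RAs as the people trained to administer the surveys.
- **How follow-up is taken.** Methods, 6. Subject Follow-up says that assessments "will be conducted at baseline (after enrollment but prior to randomization) and by phone at 3 and 6 months".
- **Tablet use.** Internet Access: "We will provide tablet devices to all participating caregivers" and "Tablets are versatile, allowing privacy for coaching sessions and website access to those in the HI group". Methods, 4. Administration of Surveys and/or Process: "Health coaching sessions will be provided through the tablets via Zoom conferencing software". Study Procedures, 1. Detailed Description says of the Health Information (HI) site: "which will be the only content provided to caregivers in the control group".
- **Set-up.** Subject Recruitment and Screening places training after randomisation: "At that time, participants will be trained in tablet use and how to access the Health Information website". Other sections give this task to research staff without naming a role.

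**The concern.** The job title that must stay blinded is also the one that caregivers are told to phone when the tablet fails. A ViCCY caregiver who cannot join a coaching session, and says so, has disclosed the arm. The leak runs one way. Both arms use the HI website, so a call about the website identifies nobody, while a call about a coaching session identifies ViCCY.

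The route is separate from the sentence under Method for Assigning Subjects to Groups that has the Project Manager notify study staff of the assignment. Correcting that sentence alone would leave the help line open.

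The Aim 1 outcomes are self-report scales taken by phone at follow-up, and the RA has some discretion in taking them. The Risks section allows data collection to be stopped, postponed or cut to the essential items when a caregiver is tired or distressed. An RA who knows the arm could, without intending to, influence how answers are given and which secondary outcomes go missing. With 15 caregivers per arm, one affected caregiver is 1/15 = 6.7% of the arm.

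**Working it through.** The plan gives no figure on this point, so there is none to reproduce. The check sets the sections side by side.

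1. *Is the help-line role also an outcome-collecting role?* By title, yes. Internet Access names the research assistant, and the Risks section has RAs administer the surveys. Whether it is the same individual for the same caregiver is not stated.
2. *Does tablet use differ by arm?* Yes. Coaching by video belongs to ViCCY only; the control arm has the HI content alone.
3. *Must that role be blinded?* Yes, until data lock, under Method for Assigning Subjects to Groups.
4. *Is there a safeguard?* None was found. No section separates a support RA from an assessing RA, sends coaching-related calls elsewhere, asks caregivers not to mention their arm, or checks whether the blind held.
5. *Does the plan apply such a safeguard elsewhere?* Yes. The Stress paragraph routes significant distress to the Project Manager and gives as the reason that the PI is blinded. The technology line has no matching arrangement.

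Three things must all happen for the blind to fail by this route: a ViCCY caregiver calls, the call reveals coaching, and the person who takes it later assesses that caregiver. The documents give no probability for any of them.

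The only possible arithmetic is therefore conditional. Let q be the assumed chance that one coaching session leads to a call meeting all three conditions. With 10 planned sessions, treated as independent, the chance of at least one such call is 1 − (1 − q)^10:

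| Assumed q | 1 − (1 − q)^10 | × 15 ViCCY caregivers |
|---|---|---|
| 0.02 | 0.183 | 2.7 |
| 0.05 | 0.401 | 6.0 |
| 0.10 | 0.651 | 9.8 |

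The table shows how a small per-session chance accumulates over 10 sessions. It does not estimate what will happen in this trial, and it says nothing about the size of any bias in the Self-Care Inventory.

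**The case against.** The case on the other side has several parts.

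- **Unblinding is not established.** A reader might infer that the outcome collector will learn the arm. The documents do not go that far. There are several RAs, a coordinator is also to be hired, and the help-line RA need not assess the caller. A caregiver who cannot join a session may also turn to the coach, who is chosen partly for ease with technology and checks in between sessions. This stands: the supported statement is that the collector can learn the arm.
- **Blinding is not the only guard.** RAs are trained not to prompt, to follow a standardised protocol and to practise every test. Consistency is reviewed at staff meetings, and retraining is annual. This stands in part. Training limits interviewer influence, but it does not restore the promised blind.
- **Set-up training need not unblind.** It is tempting to say that training a caregiver in video calls reveals the arm. The plan describes the same training for both arms, tablet use and website access, and gives it to research staff generally. This stands: training is at most a further occasion for disclosure.
- **Other threats are larger.** Caregivers know their arm and report their own outcomes, and the notification of study staff is a more direct route to unblinding. Both are true. Neither is a reason to leave open a route that costs almost nothing to close.

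**Conclusion.** The point holds as a possible and unmanaged route to unblinding, open mainly in the ViCCY arm. It rests on reading RA as the research assistant named under Internet Access, and on the absence of any stated separation of duties.

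Its size is unknown. A reader might take 3, 6 or 10 of 15 caregivers from the table as a forecast. The documents do not support that, because the values of q are assumptions and sessions are treated as independent. Nor can any effect on the treatment estimate be calculated. Bias from self-report by unblinded caregivers would remain after any change. This is a cheap improvement to a stated safeguard; it does not show that the blind will fail.

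**What to change.** 1. Under Internet Access, replace the RA's number with that of the Project Manager, who already opens the allocation envelopes, or of another existing staff member who takes no outcome data. The Project Manager also oversees data collection and meets the RAs regularly, so the text should say that what is learned on support calls is not passed to them.
2. Have the same person do the tablet set-up and training after randomisation, and name that role in Subject Recruitment and Screening, Administration of Surveys and/or Process, Consent Process, and Internet Access.
3. Have the RA log any accidental unblinding, or record a guess of arm, after each phone assessment, so that the blind can be checked.

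Leave the mode of follow-up as it is. Moving the 3- and 6-month assessments to an electronic link with phone as back-up would mix modes of primary-outcome collection in a trial of 30 caregivers, and this point does not require it.

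The cost is a change of phone number, a reassignment of tasks among existing staff and a short entry per assessment. The downside is more calls for the Project Manager.
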